8.2.1.2.2. Per-Protocol (PP) Analysis Set for anti-HIV Efficacy Analysis

The secondary analysis set for anti-HIV efficacy analyses is defined as the per-protocol (PP) analysis set for anti-HIV efficacy analysis, which will include all participants who (1) are randomized into the study, (2) have received at least 1 dose of study treatment, and (3) have not committed any major protocol violation, including the violation of key entry criteria. Participants will be grouped according to the treatment they actually received.

Participants meeting any of the following criteria will be excluded from the Week 24 PP analysis set for anti-HIV efficacy analysis:

- Participants who do not have on-treatment HIV-1 RNA in the Week 24 analysis window, except when missing due to discontinuation of study treatment for lack of efficacy.
- Participants who meet the exclusion criterion for receiving ongoing therapy with any of the medications listed in the table in protocol Section 4.3 including drugs not to be used with bictegravir.
- Nonadherence to study treatment: participants with adherence rate for active study treatment up to the Week 24 Visit below the 2.5th percentile
- Participants who do not meet the inclusion criteria for history of 3 or more TAMs (M41L, D67N, K70R, L210W, T215F/Y, and K219Q/E/N/R), T69-insertions, or K65R/E/N in RT, including pre-existing mutations that are detected post-baseline

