8.5. Efficacy Analysis

8.5.1. Primary Analysis

The primary analysis will consist of a non-inferiority test of switching to FDC of B/F/TAF versus SBR, with respect to the proportion of participants with HIV-1 RNA \geq 50 copies/mL at Week 24, as defined by the US FDA-defined snapshot algorithm. The primary analysis of the efficacy endpoint will be based on the FAS.

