8.5.1.1. US FDA-defined Snapshot Algorithm

All HIV-1 RNA data collected on-treatment (ie, including data collected up to 1 day after the last dose date of study drug) will be used in the snapshot algorithm. Virologic outcome will be defined as the following categories:

- **HIV-1 RNA < 50 copies/mL:** this includes participants who have the last available on-treatment HIV-1 RNA < 50 copies/mL in the Week 24 analysis window
- **HIV-1 RNA ≥ 50 copies/mL:** this includes participants
 - a) Who have the last available on-treatment HIV-1 RNA ≥ 50 copies/mL in the Week 24 analysis window, or
 - b) Who do not have on-treatment HIV-1 RNA data in the Week 24 analysis window and
 1. Who discontinue study treatment prior to or in the Week 24 analysis window due to lack of efficacy, or
 2. Who discontinue study treatment prior to or in the Week 24 analysis window due to reason other than lack of efficacy and have the last available on-treatment HIV-1 RNA ≥ 50 copies/mL
- **No Virologic Data in the Week 24 Analysis Window:** this includes participants who do not have on-treatment HIV-1 RNA data in the Week 24 analysis window because of the following:
 - a) Discontinuation of study treatment prior to or in the Week 24 analysis window due to reasons other than lack of efficacy and the last available on-treatment HIV-1 RNA < 50 copies/mL, or
 - b) Missing data during the window but on study treatment

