8.5.1.2. Analysis of Primary Efficacy Endpoint

The null hypothesis is that the proportion of participants achieving HIV-1 RNA < 50 copies/mL (as defined by the US FDA-defined snapshot algorithm) at Week 24 in B/F/TAF is at least 6% lower than the response rate in SBR; the alternative hypothesis is that the response rate in B/F/TAF is less than 6% lower than that in SBR.

Non-inferiority will be assessed using the conventional confidence interval (CI) approach. The point estimate of treatment difference (B/F/TAF – SBR) and the associated 2-sided 95% CI will be constructed based on the exact method.

It will be concluded that FDC of B/F/TAF is non-inferior to SBR if the upper bound of the 2-sided 95% CI of the difference between treatment groups [B/F/TAF – SBR] in the percentage of participants with HIV-1 RNA \geq 50 copies/mL is less than 6% (i.e., a margin of 6% is applied to non-inferiority assessment).

If non-inferiority of B/F/TAF to SBR is established, the upper bound of the 95% CI will be compared to 0; if the upper bound of the 95% CI is less than 0, superiority of B/F/TAF over SBR will be established.

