8.8. Sample Size

Sample sizes of 320 in B/F/TAF FDC and 160 in SBR Group achieve approximately 89% power to detect a non-inferiority margin difference between the group proportions of 0.06 for HIV-1 RNA \geq 50 copies/mL at Week 24. The assumed reference group proportion is 0.04. The treatment group proportion is assumed to be 0.10 under the hypothesis of inferiority. The power is computed for the case when the actual treatment group difference is zero (treatment = reference). The test statistic used is the one-sided Score test (Farrington & Manning) with the significance level of 0.025.

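### The Week 24 per-protocol set drops some participants whom the snapshot algorithm has already classified as HIV-1 RNA ≥ 50 copies/mL, which weakens it as secondary support for non-inferiority

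*Protocol*

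**What the plan says.** Protocol Section 8.5.1.1 defines the outcome. Among participants with no on-treatment HIV-1 RNA in the Week 24 window, it places two kinds in the failure category. Category b)1 holds those who stopped for lack of efficacy. Category b)2 holds those who stopped "due to reason other than lack of efficacy and have the last available on-treatment HIV-1 RNA ≥ 50 copies/mL". On-treatment data are those "including data collected up to 1 day after the last dose date of study drug".

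Protocol Section 8.2.1.2.2 defines the PP set. One bullet removes anyone lacking an on-treatment result in that same window, and the only carve-out reads "except when missing due to discontinuation of study treatment for lack of efficacy". Separate bullets remove participants for prohibited medication, for adherence below the 2.5th percentile and for disallowed mutations.

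On the role of the two sets, Section 8.5.1 says "The primary analysis of the efficacy endpoint will be based on the FAS", and Section 8.2.1.2.2 says "The secondary analysis set for anti-HIV efficacy analyses is defined as the per-protocol (PP) analysis set". Section 8.5 gives no PP analysis and no PP decision rule. Section 8.5.1.2 states the criterion: "a margin of 6% is applied to non-inferiority assessment".

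The supplied SAP covers the final analysis only and defines no PP set. Its Appendix 6 (item 10) has listing rows for stops due to adverse event or death, and due to other reasons, with last RNA above 50. Non-compliance is among the other reasons. SAP Section 1 refers the primary and secondary efficacy analyses to a Week 48 SAP.

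**The concern.** The PP exception retains b)1 and omits b)2. A participant who rebounds, is recorded as stopping for non-compliance, own decision or an adverse event, and has no on-treatment value in the window is a failure in the FAS and absent from the PP set, from numerator and denominator alike. The outcome is not missing, because the algorithm has already assigned it. The lack-of-efficacy exception suggests that virologic failures were meant to stay, and no supplied text explains why b)2 is left out.

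The route is open in practice. Protocol Section 6.8 lists lack of efficacy and non-compliance as separate reasons for stopping, and Section 6.13.1 allows a rebounding participant to be discontinued for ongoing non-compliance at the investigator's discretion.

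At stake is how far a PP result can support a non-inferiority finding. When the arms truly differ, removing failures pulls the PP difference towards zero, even if the same share is lost in each arm.

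**Working it through.** **Inputs.** From Protocol Section 8.8: 320 versus 160 participants, reference failure rate 0.04, test rate 0.10 at the margin, margin 0.06. On the test, "The test statistic used is the one-sided Score test (Farrington & Manning) with the significance level of 0.025". The share s of failures that fall in b)2 is not in the documents; 10% to 30% is an assumption.

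**1. Reproducing the plan's power.** With failure rate 0.04 in both arms, the Farrington-Manning restricted estimates are 0.0794 and 0.0194.
- s0 = √(0.0794 × 0.9206/320 + 0.0194 × 0.9806/160) = 0.01865
- s1 = √(0.04 × 0.96 × (1/320 + 1/160)) = 0.01897
- Power = Φ((0.06 − 1.96 × 0.01865)/0.01897) = Φ(1.236) = 89.2%, against the stated 89%.

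Full binomial enumeration of the same test gives power 91.5% and actual alpha 0.0260, against 91% and 0.026 in SAP Table 1-1.

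**2. The PP set as written, at true rates of 10% versus 4%.** If a share s of failures leaves an arm of size n with failure rate p:
- remaining size: n(1 − ps)
- remaining failure rate: p(1 − s)/(1 − ps)

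For s = 10% in both arms, the sizes are 320 × 0.99 = 317 and 160 × 0.996 = 159. The rates are 0.09/0.99 = 9.1% and 0.036/0.996 = 3.6%. Enumerating the score test on the rounded expected sizes, and ignoring the other PP exclusions, gives:

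| b)2 share of failures | Sizes | Rates | Difference (points) | Chance of meeting the 6% margin |
|---|---|---|---|---|
| 0 | 320, 160 | 10.0%, 4.0% | 6.0 | 2.6% |
| 10% in both arms | 317, 159 | 9.1%, 3.6% | 5.5 | 4.6% |
| 20% in both arms | 314, 159 | 8.2%, 3.2% | 4.9 | 7.3% |
| 30% in both arms | 310, 158 | 7.2%, 2.8% | 4.4 | 12.4% |
| 10%, B/F/TAF only | 317, 160 | 9.1%, 4.0% | 5.1 | 6.1% |
| 20%, B/F/TAF only | 314, 160 | 8.2%, 4.0% | 4.2 | 13.6% |
| 30%, B/F/TAF only | 310, 160 | 7.2%, 4.0% | 3.2 | 26.0% |

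In counts, the expected failures at these rates are 32 and 6.4. Losing 2 from B/F/TAF and none from SBR (30/318 versus 4%) gives 4.7%. Losing 5 and 1 gives 6.0%; that is an equal share, since 5/32 = 1/6.4 = 15.6%.

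**3. Direction.** Losses only in SBR work the other way. At s = 10% in SBR alone the expected difference is 10.0 − 3.6 = 6.4 points.

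**4. Single data sets (upper score bound of the 95% interval).**
- 19/320 versus 6/160: 6.01%, which misses the margin. Without one b)2 failure in B/F/TAF, 18/319 versus 6/160: 5.67%, which meets it.
- At the planned rate, 13/320 versus 6/160: 3.78%. Losing 2 and 1 gives 3.54%; losing 3 and 0 gives 2.68%. All are well inside the margin.

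The protocol's interval is an exact method that it does not name, so its bounds will differ somewhat from these score bounds.

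**The case against.** The strongest reply is that nothing in the plan is decided on the PP set. The FAS alone settles non-inferiority, so the percentages above are not error rates of any planned decision. This stands. A reader might infer that the trial's type I error is inflated, or that a confirmatory test is compromised; the documents support neither, because the PP set is a secondary set with no success criterion.

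The number affected may also be small. A participant must stop, have no on-treatment value anywhere in the window, have a last on-treatment value of at least 50 copies/mL, and not be recorded as lack of efficacy. Anyone viremic on treatment inside the window stays in the PP set as a failure. In Protocol Table 1-2, failures of all kinds at Week 48 were 2% or less, which is about 6 of 320. This stands too and limits the practical size of the problem.

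A reader might also infer that harm arises only if open-label investigators code reasons differently by arm. The calculation does not support that: equal shares lost in both arms already raise 2.6% to between 4.6% and 12.4%. Unequal losses concentrated in B/F/TAF are worse, but nothing in the documents shows that such coding would occur.

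Finally, the Week 48 SAP might contain a revised PP definition. It was not supplied, so this can be neither confirmed nor excluded.

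**Conclusion.** The two definitions do not match: as written, the PP set removes b)2 failures, and no supplied text restores them. The consequence is confined to the PP result, which becomes easier to satisfy when B/F/TAF is truly worse and so gives weaker support than it appears to. If the true rates are equal, losing equal shares leaves the expected difference at zero.

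The sizes rest on the assumed b)2 shares, true rates exactly at the margin, the score test, and no other PP exclusions. At the failure rates of the earlier switch studies, perhaps only a handful of participants, or none, would be affected. The change is worth making because it is cheap and removes the ambiguity; it is not needed to protect the primary conclusion.

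**What to change.** In Protocol Section 8.2.1.2.2, replace the lack-of-efficacy exception with: *except participants classified as HIV-1 RNA ≥ 50 copies/mL at Week 24 by the snapshot algorithm*. Leave the exclusions for non-adherence, prohibited medication and disallowed mutations in force. A b)2 failure who also meets one of those is still excluded, for that stated reason. Report b)2 counts by arm. If the Week 24 analysis has already been run, add a PP result with these participants restored, after checking the PP definition in the Week 48 SAP.

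The cost is one phrase and no new data. There is a small downside: suppressed participants without window data remain excluded while failures without window data are kept, so PP membership depends somewhat more on outcome and PP failure percentages rise slightly. Reporting the FAS alongside, as planned, lets a reader see this.

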- Have no documented or suspected resistance to INSTIs and no history of virologic failure on an INSTI containing regimen (2 consecutive HIV-1 RNA ≥ 50 copies/mL after achieving < 50 copies/mL while on an INSTI-containing regimen).
- History of 1-2 thymidine analogue mutations (TAMs), M184V/I, and any other RT substitutions are allowed, with the following exceptions: History of 3 or more TAMs (M41L, D67N, K70R, L210W, T215F/Y, and K219Q/E/N/R), T69-insertions, or K65R/E/N in RT will be excluded.
- Documented plasma HIV-1 RNA < 50 copies/mL during treatment with the baseline regimen for a minimum period of 6 months and at least the last two HIV-1 RNA measurements prior to the Screening visit
- HIV-1 RNA levels < 50 copies/mL at Screening
- Estimated glomerular filtration rate (eGFR) ≥ 50 mL/min according to the Cockcroft-Gault formula for creatinine clearance

Study Procedures/ Frequency:	
After Screening procedures, eligible participants will be randomized 2:1 to Treatment Group 1 or Treatment Group 2 and treated for 48 weeks. Following the Day 1 visit, participants will be required to return for study visits at Weeks 4, 12, 24, 36, and 48. Participants randomized to SBR will have an additional visit at Week 28.
 
Laboratory analyses (chemistry, hematology, and urinalysis), HIV-1 RNA, CD4+ cell count, assessment of adverse events and concomitant medications, and complete or symptom directed physical examinations will be performed at Screening, Day 1 and subsequent study visits. Whole blood for HIV-1 DNA archive testing will be collected at Day 1 for all participants and at Week 24 for all participants in Treatment Group 2.
 
Historical HIV-1 RNA genotypes will be collected if available.

Test Product, Dose, and Mode of Administration:	FDC of bicitegravir 50 mg / emtricitabine 200 mg / tenofovir alafenamide 25 mg (B/F/TAF) administered orally, once daily, without regard to food
Reference Therapy, Dose, and Mode of Administration:	Baseline regimen consisting of 2 NRTIs and an allowed 3 rd agent taken as prescribed
Criteria for Evaluation:	
Safety:	Adverse events, clinical laboratory tests, and tolerability of treatment regimens

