4.3. Exclusion Criteria

Participants who meet *any* of the following exclusion criteria are not to be enrolled in this study.

- 1) History of 3 or more TAMs (M41L, D67N, K70R, L210W, T215F/Y, and K219Q/E/N/R), T69-insertions, or K65R/E/N in RT will be excluded
- 2) No desire to switch from current ARVs
- 3) An opportunistic illness indicative of stage 3 HIV diagnosed within the 30 days prior to screening (refer to [Appendix 5](#))
- 4) Participants experiencing decompensated cirrhosis (e.g., ascites, encephalopathy, or variceal bleeding)
- 5) Have been treated with immunosuppressant therapies or chemotherapeutic agents within 3 months of study screening, or expected to receive these agents or systemic steroids during the study (eg, corticosteroids, immunoglobulins, and other immune- or cytokine-based therapies)
- 6) Malignancy within 5 years of screening other than cutaneous Kaposi's sarcoma, completely resected non-melanoma skin cancer (basal cell carcinoma or non-invasive cutaneous squamous carcinoma), or completely resected carcinoma in-situ of the cervix (CIN 3) or anus (AIN 3). A prior malignancy treated with curative therapy and for which there has been no evidence of disease for at least five years prior to screening is allowed.
- 7) Current alcohol or substance use judged by the Investigator to potentially interfere with participant study compliance
- 8) Active, serious infections (other than HIV-1 infection) requiring antibiotic or antifungal therapy within 30 days prior to Day 1
- 9) Participation in any other clinical trial, including observational studies, without prior approval from the sponsor is prohibited while participating in this trial
- 10) Any other clinical condition or prior therapy that, in the opinion of the Investigator, would make the participant unsuitable for the study or unable to comply with the dosing requirements
- 11) Known hypersensitivity to FDC of B/F/TAF tablets, their metabolites, or formulation excipient
- 12) Females who are pregnant (as confirmed by positive serum pregnancy test)
- 13) Females who are breastfeeding
- 14) Participants receiving ongoing therapy with any of the following medications in the table below, including drugs not to be used with FDC of B/F/TAF

Drug Class	Agents Disallowed*
Antiarrhythmic Agent	Dofetilide
Anticonvulsants	Phenobarbital, Phenytoin, Carbamazepine, Oxcarbazepine
Antimycobacterials	Rifampin, Rifapentine, Rifabutin

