6.2. Pretreatment Assessments

6.2.1. Screening Visit

Participants will be screened within 30 days before Day 1 to determine eligibility for participation in the study. The following will be performed and documented at screening:

- Obtain written informed consent(s)
- Obtain demographic information, including gender at birth, sexual orientation, and gender identity
- Obtain screening number in IWRS
- Obtain medical history including history of HIV-1 disease-related events, and prior medications within 30 days of the screening visit
- If available, obtain documentation of historical genotype(s) (**not required for entry to study**)
- Complete physical examination (urogenital/anorectal exams will be performed at the discretion of the Investigator)
- 12-lead ECG performed supine
- Height
- Vital signs measurement (blood pressure, pulse, respiration rate, and temperature), including weight
- Obtain blood and urine samples as described in Sections [6.9.1](#) and [6.9.2](#)
- Review concomitant medications
- Record any SAEs and all AEs related to protocol mandated procedures occurring after signing of the consent form

Participants meeting all of the inclusion criteria, and none of the exclusion criteria, will return to the clinic within 30 days after screening for the Day 1 Visit. Participants randomized to Treatment Group 1 must continue to take their prior treatment regimen up until the day before their scheduled Day 1 visit. Participants randomized to Treatment Group 2 will continue to take their prior treatment regimen until they switch to FDC of B/F/TAF at Week 24.

From the time of obtaining informed consent through the first administration of study treatment, record all SAEs, as well as any AEs related to protocol-mandated procedures on the adverse events eCRF. All other untoward medical occurrences observed during the screening period, including exacerbation or changes in medical history are to be captured on the medical history eCRF. See Section 7 Adverse Events and Toxicity Management for additional details.

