— HBV blood panel (**Screening and Week 48**): Hepatitis B virus surface antigen (HBsAg), Hepatitis B virus surface antibody (HBsAb) and Hepatitis B virus core antibody (HbcAb)

The following tests will be conducted by the central laboratory if the following criteria are met:

- *If positive HBsAg*: reflex testing for plasma HBV DNA, Hepatitis B virus e-antigen (HBeAg) (if negative, reflex Hepatitis B virus e-Antibody [HBeAb]), and quantitative HBsAg

- *If positive HBcAb with negative HBsAg and negative HBsAb*: reflex testing for plasma HBV DNA (if positive, reflex HBeAg). If HBeAg is performed and found to be negative, reflex HBeAb
- Plasma HBV DNA for patients who are HBV co-infected (**Day 1, Week 24, Week 48, and ESDD**)

HBV coinfection, for the purposes of this study, is defined as any one of the following two criteria on or prior to Day 1:
 1. Positive HBsAg
 2. Negative HBsAg, negative HBsAb, positive HBcAb and quantifiable HBV DNA (HBV DNA ≥ 20 IU/mL)
- HCV antibody (Ab) serology (**Screening, Week 48, and Week 72**). Participants who are HCVAb positive will have a HCV RNA test performed.
- Mandatory Whole blood for HIV-1 DNA archive testing (**Day 1 for all participants, and at Week 24 for participants randomized to SBR only**)
- **CCI** [REDACTED]
- Plasma and serum storage sample for safety, virology, or PK testing (Not collected at Screening and 30-day Follow-up Visits)

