6.13.1. Management of Virologic Rebound

Participants who meet the criteria listed below will be considered to have virologic rebound:

- At any post Day 1 visit, a rebound in HIV-1 RNA ≥ 50 copies/mL

Following the virologic rebound, participants will be asked to return to the clinic for a scheduled or unscheduled blood draw (within 2 to 3 weeks after the date of the original test that resulted in HIV-1 RNA ≥ 50 copies/mL). Participants with HIV-1 RNA values between 50-200 copies/mL should follow the algorithm in [Figure 6-1](#). If virologic rebound is confirmed at the scheduled or unscheduled visit and the HIV-1 RNA is ≥ 200 copies/mL, the plasma sample from the confirmation visit will be the primary sample used for HIV-1 genotypic and phenotypic testing. After a participant's first post-Day 1 resistance test, additional testing will be conducted on a case-by-case basis. Any participant may be discontinued at Investigator's discretion or per local treatment guidelines.

[figure not shown]
If no resistance to study treatment is detected from the genotype or phenotype, the participant may remain on study treatment and HIV-1 RNA should be analyzed at a new visit (within 2 to 3 weeks after date of test with HIV-1 RNA ≥ 50 copies/mL). Investigators should carefully evaluate the benefits and risks of remaining on study treatment for each individual participant and document this assessment in the on-site medical record.

Participants who are noncompliant on an ongoing basis will be considered for discontinuation per the Investigator’s discretion or local treatment guidelines. Investigators who opt to discontinue study treatment for an individual participant must discuss with the Medical Monitor prior to study drug discontinuation.

For participants who are off study treatment but remain on study, it will be the Investigator’s discretion to manage virologic rebound.

Please refer to [Figure 6-1](#) for the management of participants who meet the criteria for virologic rebound.

Figure 6-1. Virologic Rebound Schema

a. If the HIV-1 RNA is between 50 and 200 copies/mL, a reflex HIV-1 RNA repeat test will be conducted on stored plasma if available. If the repeat result is < 50 copies/mL, then no further action is required. If the repeat result is ≥ 50 copies/mL then proceed to the scheduled or unscheduled visit 2 – 3 weeks later.

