- b. If the HIV-1 RNA is < 50 copies/mL then no further action is required. If the HIV-1 RNA is between 50 and 200 copies/mL, a reflex HIV-1 RNA repeat test will be conducted on stored plasma if available. If the repeat result is < 50 copies/mL, then no further action is required. If the repeat result is between 50 and 200 copies/mL this is protocol defined confirmed virologic failure and the Medical Monitor should be consulted. If the repeat result is ≥ 200 copies/mL, then a Genotype and Phenotype test will be ordered.
- c. If virologic rebound is confirmed and the last HIV-1 RNA is ≥ 200 copies/mL, the HIV-1 genotype and phenotype (reverse transcriptase, protease and integrase) will be analyzed. If the genotype and phenotype assay fails, Investigator reviews study treatment continuation/discontinuation options and discuss with the Medical Monitor prior to study treatment discontinuation.
- d. If no new resistance to study treatment is detected, HIV-1 RNA will be repeated 2 – 3 weeks later. Investigator reviews study treatment continuation/discontinuation options and discuss with the Medical Monitor prior to study treatment discontinuation. The participant will remain in the study.
- e. A new ARV regimen may be configured, at the Investigator's discretion and the participant will remain in the study.

6.13.2. Participants with HIV-1 RNA ≥ 50 copies/mL at Study Drug Discontinuation, Week 24, or Week 48

Participants with HIV-1 RNA ≥ 50 copies/mL at study drug discontinuation, last visit, or last Week 24 or Week 48 result will be considered virologic failures. Participants with HIV-1 RNA ≥ 50 copies/mL at Week 24 or Week 48 will be asked to return for an unscheduled visit within the visit window for a retest.

Participants with HIV-1 RNA ≥ 200 copies/mL at study drug discontinuation, last visit, or Week 24 or Week 48 visit, will also have resistance testing conducted.

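### The per-protocol rule on excluded RT mutations does not limit its source to tests given to everyone, so exclusion can depend on outcome and possibly on arm

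*Protocol*

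**What the plan says.** - **The PP rule.** Protocol 8.2.1.2.2: "The secondary analysis set for anti-HIV efficacy analyses is defined as the per-protocol (PP) analysis set". One bullet drops from the Week 24 PP set participants who breach the mutation criterion, "T69-insertions, or K65R/E/N in RT, including pre-existing mutations that are detected post-baseline". It gives no assay, sample or latest date. It also calls the criterion an inclusion criterion, although it is exclusion criterion 1 in Protocol 4.3: "History of 3 or more TAMs (M41L, D67N, K70R, L210W, T215F/Y, and K219Q/E/N/R), T69-insertions, or K65R/E/N in RT will be excluded".
- **Entry.** Protocol 6.2.1 collects a historical genotype only where one exists and does not make it a condition of entry.
- **DNA archive.** Protocol 6.9.1 makes whole blood for archive testing mandatory at "Day 1 for all participants, and at Week 24 for participants randomized to SBR only". The synopsis and Appendix 2 agree.
- **Plasma resistance tests.** Under Protocol 6.13.1, when rebound is confirmed at 200 copies/mL or more, "the plasma sample from the confirmation visit will be the primary sample used for HIV-1 genotypic and phenotypic testing". Under 6.13.2, participants at 200 copies/mL or more at study drug discontinuation, last visit, Week 24 or Week 48 "will also have resistance testing conducted". Appendix 2, footnote q, has confirmed failure with a value above 200.
- **SAP.** The supplied SAP covers the final analysis and defines no PP set. Its Section 1 refers to a Week 48 SAP for the primary and secondary endpoints, and Section 2.1.1 says the Week 24 analysis has been done.

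**The concern.** An eligibility rule applied after randomisation is harmless when every participant gets the same scrutiny. Here the bullet reaches past Day 1, and the resistance tests scheduled on later samples are not given to everyone. One is triggered by viraemia, which is close to the primary endpoint: a value of 200 copies/mL or more at Week 24 normally makes the participant a snapshot failure (Protocol 8.5.1.1) and also orders the test that could remove them from the PP set. A participant with the same undetected mutation who stays suppressed is not tested again and stays in. Deleting failures while keeping the matching successes lowers the PP failure rate.

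Two further points follow. If the Week 24 archive sample were used, SBR participants would have a second chance of exclusion that B/F/TAF participants do not have. And deciding whether a mutation first seen at failure was pre-existing or emergent would be done in an open-label trial with arm and outcome known. At stake is the value of the PP set as a check on the non-inferiority result.

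**Working it through.** **Step 1: who can be detected, and when.** From Protocol 6.2.1, 6.9.1, 6.13.1 and 6.13.2:

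| Source | B/F/TAF, <200 | B/F/TAF, ≥200 | SBR, <200 | SBR, ≥200 |
|---|---|---|---|---|
| Historical genotype | if it exists | if it exists | if it exists | if it exists |
| Day 1 DNA archive | yes | yes | yes | yes |
| Triggered plasma genotype | no | yes | no | yes |
| Week 24 DNA archive | no | no | yes | yes |

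(Columns: HIV-1 RNA in copies/mL at a triggering visit.) The first two rows depend on neither arm nor outcome. The third depends on outcome and the fourth on arm. The PP bullet does not say which rows count.

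**Step 2: the plan's own figure.** Inputs from Protocol 8.8: 320 versus 160, 4% in both arms, margin 6 points, one-sided 0.025. The standard error is √[0.04 × 0.96 × (1/320 + 1/160)] = 0.01897. The unpooled approximation gives Φ(0.06/0.01897 − 1.96) = Φ(1.20) = 88.5%. The Farrington-Manning test with its restricted variance gives 89.2%, matching the stated 89%. Exact enumeration gives 91.5% with actual alpha 0.026, in line with the first row of SAP Table 1-1. This power does not depend on the PP rule; it confirms the inputs used below.

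**Step 3: illustration with assumed inputs.** Let q be the share of participants with an excluded mutation missed by both history and the Day 1 archive, and f their failure rate, the same in both arms. Others fail at 4%. Neither q nor f is in the documents; I take q from 1% to 5% and f from 4% to 20%. The true difference is 0.

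Worst reading: B/F/TAF carriers are removed only if they fail, and all SBR carriers are removed at Week 24.

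- B/F/TAF PP rate = 0.04(1 − q)/(1 − qf)
- SBR PP rate = 0.04(1 − q)/(1 − q) = 4.00%

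| q | f | B/F/TAF PP | Difference (points) |
|---|---|---|---|
| 1% | 4% | 3.96% | −0.04 |
| 1% | 20% | 3.97% | −0.03 |
| 3% | 4% | 3.88% | −0.12 |
| 3% | 20% | 3.90% | −0.10 |
| 5% | 4% | 3.81% | −0.19 |
| 5% | 20% | 3.84% | −0.16 |

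If the Week 24 SBR sample is not used, the B/F/TAF formula applies to both arms. Each rate is then too low (at q = 5%, f = 20%: 0.04 × 0.95 + 0.05 × 0.20 = 4.8% true, 3.84% in the PP set), but the difference stays at 0. If only history and the Day 1 archive count, these carriers stay in both arms and nothing shifts. The range does not cover carriers who fail at different rates in the two arms, where removing only the failing ones would hide part of a real difference; the documents give nothing to size that.

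**Step 4: what one exclusion does.** Expected failures are 0.04 × 320 = 12.8 and 0.04 × 160 = 6.4. With 13/320 versus 6/160, the upper 95% score limit for the difference is 3.8%. Removing one B/F/TAF failure (12/319) gives 3.4%, and removing two (11/318) gives 3.1%. These are score limits, whereas the protocol plans an exact method. In the other direction, removing one SBR failure moves that arm from 4.0% to (6.4 − 1)/159 = 3.4%, against non-inferiority.

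**The case against.** The strongest reply is that an even-handed source already exists. Every participant gives the Day 1 archive sample, archive testing is not a screening assessment, and eligibility is confirmed before Day 1 (Protocol 5.1, 6.2.1, 6.4). The result therefore arrives after entry, and a Day 1 sample read later is a natural meaning of the bullet. This stands as a possible reading. A reader might infer from the bullet that the whole eligibility check depends on outcome and arm; the documents do not support that. Only the part resting on later samples does.

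Other replies also stand:

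- No passage says that the Week 24 SBR sample feeds the PP set. It is drawn at the delayed switch and may simply be that group's baseline before B/F/TAF.
- Virologic failure is 50 copies/mL or more (Protocol 6.13), so failures at 50 to 199 trigger no genotype and cannot be removed this way.
- A mutation first seen at failure, with no earlier evidence, could be classed as emergent, and the participant would stay in.
- The PP set is secondary and carries no decision rule.
- The Week 48 SAP, not available here, may settle the matter.

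A reader might also infer a bias of 0.6 to 0.9 points, by removing two or three B/F/TAF failures: (12.8 − 2)/318 = 3.4% or (12.8 − 3)/317 = 3.1%, from 4.0%. That needs 2/12.8 = 16% to 3/12.8 = 23% of expected failures to carry an excluded mutation missed by both history and the Day 1 archive. The documents give no such figure.

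None of this limits the bullet to the Day 1 or historical source. By contrast, SAP 3.1.2 ties the resistance exclusion in its B/F/TAF full analysis set to historical data.

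**Conclusion.** The point holds for the secondary PP set. As worded, the rule lets a test triggered by HIV-1 RNA of 200 copies/mL or more remove the participants who triggered it, and leaves open the use of an SBR-only sample. Dependence on outcome follows from the wording if it is applied literally; dependence on arm is only possible. The size cannot be derived from the documents. The 0.03 to 0.19 points towards non-inferiority rest on assumed carrier and failure rates, equal carrier failure in both arms, every failing carrier being genotyped and classed as pre-existing, and use of the Week 24 SBR sample. That is small against 6 points, and SBR exclusions can offset it. The primary conclusion is not at issue: it rests on the full analysis set, whose own resistance clause in Protocol 8.2.1.2.1 lacks the post-baseline wording.

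**What to change.** Replace the bullet with: *Participants who meet exclusion criterion 1 on the historical genotype or on the Day 1 HIV-1 DNA archive result.* Add that triggered plasma genotypes and the Week 24 SBR archive result are listed and do not determine PP membership, and that the general PP clause on key entry criteria is applied to this criterion in the same way. This also corrects the reference to inclusion criteria.

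If the sponsor prefers to keep excluding on later results, report a PP sensitivity analysis that retains those participants. Because the Week 24 analysis has already been run under a plan not among these documents, the report should state, for each participant excluded under this bullet, which source led to the exclusion.

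The cost is a few lines of text and one listing; the Day 1 sample is already mandatory in both arms. The downside is that a few participants whose excluded mutation is found only later stay in the PP set.
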